1. INTRODUCTION

This statistical analysis plan (SAP) describes the statistical analysis methods and defines key elements including variable definitions for analysis of data of Study *GS-US-313-1580* in support of the clinical study report (CSR). This SAP is based on the study protocol *amendment 6* dated *18 March 2021*. Any changes made after the finalization of the SAP will be documented in the CSR.

This study was designed to evaluate a safe and effective dosing regimen of idelalisib in subjects with relapsed or refractory Follicular Lymphoma (FL) who have no other therapeutic options. It is a randomized, open-label, multi-center global study with three treatment arms in total of 266 subjects planned. The study was terminated early due to slow enrollment, with rapidly evolving treatment options for FL as the primary reasons.

Analysis methods specified in this document take precedence over those described in protocol should there be any difference.

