1.2.2. Secondary Endpoints

- DOR, defined as the interval from the first documentation of CR or PR to the earlier of the first documentation of disease progression by independent review committee (IRC or death from any cause
- ORR by Week 24, defined as the proportion of subjects who achieve a PR or CR by Week 24
- Overall safety profile of idelalisib, including the incidence of AEs and clinically significant laboratory abnormalities, severity, timing, and relationship to idelalisib of any AEs; SAEs; or AEs leading to interruption, reduction, or discontinuation of idelalisib Time to onset of AEs of interest (AEIs) defined as the interval from the start of idelalisib treatment to the first documentation of start of AEI
- PFS, defined as the interval from randomization to the earlier of the first documentation of disease progression by IRC or death from any cause
- OS, defined as the interval from randomization to death from any cause
- Idelalisib trough (predose) and peak (1.5-hour samples) plasma concentrations assessed by validated bioanalytical method

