6.1.2. Analysis for Secondary Endpoints

The ORR by Week 24 and corresponding 95% CIs will be evaluated by treatment arm using the IRC assessments in the ITT Analysis Set.

The time-to-event efficacy endpoints including PFS, DOR, and OS will be analyzed using the Kaplan-Meier method in the ITT Set, and the analysis of DOR will include subjects who achieve a PR or CR. Analyses may also be performed for subgroups defined by potential predictors of response. The Kaplan-Meier plot will be provided for PFS and OS.

PFS and DOR Censoring rules:

- 1) Subjects who discontinued study prior to PD or death will be censored on the last tumor assessment date.
- 2) Subjects who missed ≥ 2 consecutive tumor assessments, and did not have a PD prior to missing ≥ 2 consecutive tumor assessments will be censored on the last tumor assessment date prior to missing ≥ 2 consecutive assessments.
- 3) Subjects who received new anti-cancer therapy will be censored on the last assessment date prior to receiving new anti-cancer therapy.
- 4) Subjects who are alive and do not have any on-study tumor assessments will be censored on the randomization date (applicable only for PFS)

OS censoring rules:

- 1) Subjects who do not have a recorded death date will be censored on the last known alive date.

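### PFS/DOR censoring rule 3 (SAP 6.1.2) lacks the no-prior-PD condition, so taken literally it censors IRC-documented progressions that are followed by new therapy (minor, secondary endpoints)

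*SAP*

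**What the plan says.** SAP 1.2.2 defines the two endpoints by their events. For PFS the text is: "PFS, defined as the interval from randomization to the earlier of the first documentation of disease progression by IRC or death from any cause". The DOR entry has the same form: "DOR, defined as the interval from the first documentation of CR or PR to the earlier of the first documentation of disease progression". As with PFS, it relies on the IRC's reading, and death also ends the interval. Neither definition mentions new therapy.

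SAP 6.1.2 then lists the PFS and DOR censoring rules. Three matter here:

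- Rule 1: "Subjects who discontinued study prior to PD or death will be censored on the last tumor assessment date".
- Rule 2 covers subjects who missed two or more consecutive tumor assessments and "did not have a PD prior to missing" them.
- Rule 3: "Subjects who received new anti-cancer therapy will be censored on the last assessment date prior to receiving new anti-cancer therapy".

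The fourth rule, for living subjects with no on-study assessment, plays no part. Protocol 8.5.2 names the Kaplan-Meier method for these endpoints but gives no censoring rules. Neither document states an order between events and censoring, or between one censoring rule and another.

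**The concern.** Rules 1 and 2 each exclude subjects who have already progressed. Rule 3 covers everyone who received new anti-cancer therapy, whether before or after progression. Since the two rules above it spell the condition out, a reader cannot be sure that it is implied in the third.

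PD followed by new therapy is a foreseeable sequence. Under Protocol 3.5.1, IRC-assessed progression is a reason to stop study drug, with an escalation provision for Arm B. Protocol 6.7 plans to collect later anti-tumor treatment at annual survival contacts. For such a subject the SAP gives two answers: an event under 1.2.2, and a censored time under the literal text of 6.1.2.

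The error would run in one direction. Progressions would become censored times and never the reverse, so PFS and DOR could only look longer. No formal test is planned (SAP 3.5), so the Kaplan-Meier estimates are the whole result for these endpoints.

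**Working it through.** There is no stated figure to reproduce: the documents give no PFS or DOR median, event count or re-treatment share. The check is a reading of the rules, followed by an illustration.

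**Rules side by side**

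| Sequence | SAP 1.2.2 | Rule 3, literal | Rule 3, limited to therapy before PD |
|---|---|---|---|
| IRC PD, then new therapy | Event at PD | Censored, normally at the PD scan | Event at PD |
| New therapy, no earlier PD | No event yet | Censored at last assessment before therapy | Same |
| IRC PD, no new therapy | Event at PD | Rule does not apply | Rule does not apply |

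Only the first row differs. The censoring date there is normally the PD scan because scheduled scans run until IRC-documented progression (Protocol 6.1.7). Only the PD half of the missing condition matters, since therapy cannot follow death.

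**Mechanism at one scan.** Suppose 40 of 100 subjects at risk have PD at a scan. Counted as events, S = 1 − 40/100 = 0.60. If a quarter of the 40 are later re-treated and therefore censored, S = 1 − 30/100 = 0.70. If half are, S = 1 − 20/100 = 0.80.

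**Illustration over 48 weeks**

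Inputs from the documents are the scan schedules in Protocol 6.1.7: Weeks 12, 24, 36 and 48, or before Amendment 5 Weeks 8, 16, 24, 36 and 48.

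Everything else is assumed:

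- exponential time to PD with median m, and PD dated at the next scheduled scan;
- the PD scan is the last assessment before new therapy;
- no other censoring, and subjects censored at a tied time stay in the risk set;
- a share p of progressors is re-treated;
- a share d of events is deaths without PD, placed at scan dates for simplicity.

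For a scan interval of length L weeks, q = 1 − 0.5^(L/m). Then:

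- events as defined: S = Π(1 − q);
- rule 3 taken literally: S = Π(1 − q·[d + (1 − d)(1 − p)]).

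With m = 48, L = 12 and d = 0: q = 1 − 0.5^0.25 = 0.1591. As defined, S(48) = 0.8409^4 = 0.500. With p = 0.30, S(48) = (1 − 0.1591 × 0.70)^4 = 0.8886^4 = 0.624.

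| Assumed scenario | As defined | p = 10% | p = 30% | p = 50% |
|---|---|---|---|---|
| PFS Week 48, m = 48, d = 0 | 50.0% | 53.9% | 62.4% | 71.8% |
| Same, pre-Amendment 5 scans | 50.0% | 53.8% | 62.2% | 71.6% |
| Same as first row, d = 0.2 | 50.0% | 53.1% | 59.7% | 66.9% |
| PFS Week 48, m = 36, d = 0 | 39.7% | 44.0% | 53.6% | 64.7% |
| PFS Week 48, m = 60, d = 0 | 57.4% | 60.9% | 68.4% | 76.5% |
| DOR 36 weeks after a Week-12 response, m = 48, d = 0 | 59.5% | 62.9% | 70.2% | 78.0% |

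At p = 0 the two formulas agree and the effect is zero.

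A separate simulation let deaths without PD fall at their own times (median 48 weeks to PD, median 10 years to such a death). Week-48 PFS was 0.47 with events as defined. Read literally, it was 0.57 with 25% re-treated and 0.67 with 50%. The direction is the same; the size follows the assumed inputs.

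**The case against.** The strongest reply is that the SAP already defines the event. Under 1.2.2 the interval ends at the first IRC progression, so therapy given later cannot undo it, and most programmers would take the PD first. The protocol points the same way. Section 3.5.1 continues disease assessments until progression, the end of participation or another therapy, and 3.5.2 lists progression and new therapy as separate reasons to leave. This stands as evidence of intent and is why the point is only minor. It does not repair the rule, because rules 1 and 2 state the condition, rule 3 omits it, and no sentence ranks event over censoring.

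A second reply is that rule 2 could also be read too literally. A subject who dies without PD after a clean scan has no later scans, and the rule's text mentions only PD. That is fair, and it supports adding an ordering sentence as well as mending rule 3.

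Three further inferences are tempting, and the documents do not support them:

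- **That the SAP's precedence clause makes the literal reading binding.** The clause is "Analysis methods specified in this document take precedence over those described in protocol should there be any difference". The event definitions match in both documents (SAP 1.2.2, Protocol 8.1.3), so there is no difference for it to act on. The tension lies within the SAP.
- **That records of therapy after PD are known to exist.** Protocol 6.7 shows only that collection was planned, and "The study was terminated early due to slow enrollment". How much follow-up took place is not stated.
- **That adding the missing clause settles every case.** Take a scan at Week 12, missed scans at Weeks 24 and 36, a clean scan at Week 48 and new therapy at Week 50. Rule 2 censors at Week 12 and the amended rule 3 at Week 48. An order is still needed.

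**Conclusion.** Rule 3 is wrong as written, at a minor level. Followed exactly, it censors progressions that the SAP's own definitions count as events and biases the PFS and DOR curves upward. Followed as probably intended, it does no harm.

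A reader might infer that the reported PFS or DOR is inflated. The documents do not support that: nothing shows how the endpoints were programmed. Nor do they support any particular size, since the medians, re-treatment shares and death share above are all assumed. The firm conclusions are the missing condition, the missing order, and the direction of the error if the text is applied literally.

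The consequence is confined to two descriptive secondary endpoints. ORR, Grade ≥ 4 TEAEs, OS and the sample size are untouched.

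**What to change.** Make two edits in SAP 6.1.2, for both PFS and DOR:

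- In rule 3, insert *prior to IRC-documented PD* directly after the first mention of new anti-cancer therapy, and specify that the censoring date is that of the last tumor assessment before the therapy.
- Add one sentence: *An IRC-documented PD or death that occurs before any censoring condition is met counts as an event; if more than one censoring rule applies, the earliest censoring date is used.*

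The sentence also settles the overlap of rules 2 and 3: the subject in the Week-12/Week-48 example is censored at Week 12.

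If the SAP is not reopened, check this condition in the PFS and DOR derivation and state the rule used in the CSR. The SAP gives that route: "Any changes made after the finalization of the SAP will be documented in the CSR". The cost is one clause and one sentence, or a CSR note, plus a check of one condition in the derivation program.

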7. ANALYSIS OF ADVERSE EVENTS AND LABORATORY EVALUATIONS

All AEs will be listed. The focus of AE summarization will be on treatment-emergent AEs. Safety analyses will be conducted using Safety Analysis Set, unless otherwise specified.

7.1. Adverse Events and Deaths

7.1.1. Adverse Event Dictionary

Clinical and laboratory adverse events (AEs) will be coded using the current version of Medical Dictionary for Regulatory Activities (MedDRA). System organ class (SOC), high-level group term (HLGT), high-level term (HLT), preferred term (PT), and lower-level term (LLT) will be provided in the AE dataset.

7.1.2. Adverse Event Severity

Adverse events are graded by the investigator as Grade 1, 2, 3, 4, or 5 according to Common Terminology Criteria for Adverse Events (CTCAE) Version 5.0. The severity grade of events for which the investigator did not record severity will be categorized as “missing” for tabular summaries and data listings. The missing category will be listed last in summary presentation.

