1.2. Study Endpoints

1.2.1. Primary Endpoints

- ORR, defined as the proportion of subjects who achieve a partial response (PR) or complete response (CR) by independent review committee (IRC)
- Incidence of Grade ≥ 4 treatment-emergent adverse events (TEAEs)

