2.3. Final Analysis

The final analysis will be performed after all subjects have completed or discontinued from the study, outstanding data queries have been resolved or adjudicated as unresolvable, and the data have been cleaned and finalized.

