7.1.3. Relationship of Adverse Events to Study Drug

Related AEs are those for which the investigator selected “Related” on the AE CRF to the question of “Related to Study Treatment.” Relatedness will always default to the investigator’s choice, not that of the medical monitor. Events for which the investigator did not record relationship to study drug will be considered related to study drug for summary purposes. However, by-subject data listings will show the relationship as missing.

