7.1.5.2. Incomplete Dates

If the onset date of the AE is incomplete and the AE stop date is not prior to the first dosing date of study drug, then the month and year (or year alone if month is not recorded) of onset determine whether an AE is treatment emergent. The event is considered treatment emergent if both of the following 2 criteria are met:

- The AE onset is the same as or after the month and year (or year) of the first dosing date of study drug, and
- The AE onset date is the same as or before the month and year (or year) of the date corresponding to 30 days after the date of the last dose of study drug.

An AE with completely missing onset and stop dates, or with the onset date missing and a stop date later than the first dosing date of study drug, will be considered to be treatment emergent. In addition, an AE with the onset date missing and incomplete stop date with the same or later month and year (or year alone if month is not recorded) as the first dosing date of study drug will be considered treatment emergent.

In case when the AE onset date is incomplete and needs to be imputed, the following algorithm will be followed:

- If the day is missing but the month and year are available, then the imputed day will be the first day of the month or the first dosing date if they have the same month and year, whichever is later.
- If the day and month are missing but year is available, then the imputed day and month will be 01 Jan or the first dosing date if they have the same year, whichever is later.

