7.1.6.1. Summaries of Adverse Events Incidence by Severity

The number and percentage of subjects who experienced at least 1 TEAE will be provided and summarized by SOC and PT.

The number and percentage of subjects who experienced at least 1 TEAE will be provided and summarized by PT and severity in descending order of total frequency:

- Treatment-Emergent Adverse Events by PT and Severity

For the AE categories described below, summaries will be provided by PT in descending order of total frequency:

- All Treatment-Emergent Adverse Events
- Grade 4 or Higher Treatment-Emergent Adverse Events
- Grade 3 or Higher Treatment-Emergent Adverse Events
- Treatment-Emergent Idelalisib related Adverse Events
- Treatment-Emergent Serious Adverse Events
- Treatment-Emergent Idelalisib related Serious Adverse Events
- Treatment-Emergent Adverse Events leading to discontinuation of Idelalisib
- Treatment-Emergent Adverse Events leading to temporary interruption of Idelalisib
- Treatment-Emergent Adverse Events leading to study discontinuation
- Treatment-Emergent Adverse Events leading to Death

A brief, high-level summary of AEs described above will be provided by treatment arms and by the number and percentage of subjects who experienced the above AEs.

For summaries of TEAEs by PT, multiple events will be counted only once per subject in each summary. Adverse events will be summarized and listed by PT in descending order of total frequency. For summaries by severity, the most severe severity will be used for those AEs that occurred more than once in a given subject during the study.

In addition, by-subject data listings will be provided by treatment arms and subject ID number in ascending order for the following:

- All AEs, indicating whether the event is treatment emergent
- All SAEs
- All Deaths
- All Adverse Events leading to Death
- All Adverse Events with Grade 3 or Higher
- All Adverse Events with Grade 4 or Higher

- All Adverse Events leading to discontinuation of Idelalisib
- All Adverse Events leading to temporary interruption of Idelalisib
- All Adverse Events leading to study discontinuation

A flag will be included in the listings to indicate whether the event is treatment emergent.

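### A TEAE without a recorded grade cannot enter the Grade ≥4 primary safety count, even when its fatal outcome or life-threatening seriousness settles the grade

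*SAP*

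**What the plan says.** SAP 1.2.1 makes the incidence of Grade ≥4 TEAEs a primary endpoint. SAP 7.1.6.1 reports it in a summary titled "Grade 4 or Higher Treatment-Emergent Adverse Events". Protocol 8.6.2 describes the same quantity as the number and percentage of subjects with at least one such event.

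On missing severity, SAP 7.1.2 says: "The severity grade of events for which the investigator did not record severity will be categorized as" missing, for both tables and listings. It adds: "The missing category will be listed last in summary presentation". SAP 3.6.1 leaves missing data unimputed unless a method is specified. The exceptions it lists are last dosing date, AE onset date and medication dates; severity is not among them.

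Other missing AE fields are treated differently. SAP 7.1.3: "Events for which the investigator did not record relationship to study drug will be considered related to study drug for summary purposes". Under SAP 7.1.5.2, "An AE with completely missing onset and stop dates" is taken to be treatment emergent.

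**The concern.** Severity is the field that defines the primary safety endpoint, yet of these AE fields it is the only one whose absence takes an event out of the count. For some events the grade can be read from other information: a TEAE with a fatal outcome is Grade 5 by the protocol's own scale, and one reported as life-threatening matches Grade 4. The SAP has no rule that uses this.

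No formal testing is planned (SAP 3.5), so the estimated rate and its interval are the whole result for this endpoint. Protocol 1.3 gives as a goal whether the alternative regimen has similar efficacy with less toxicity. A rule that can move a safety rate only in the favourable direction should be closed where that is cheap.

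**Working it through.** **Step 1. Does the exclusion follow from the text?** The SAP does not state it in words. It follows from four points taken together:

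- An ungraded event has a category of its own, separate from Grades 1 to 5 (SAP 7.1.2).
- No method fills in severity (SAP 3.6.1).
- The endpoint table takes only events of Grade 4 or higher (SAP 7.1.6.1).
- No section of either document assigns Grade 5 to an ungraded fatal event or Grade 4 to an ungraded life-threatening one.

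The rule in SAP 7.1.6.1 that keeps the most severe grade for a repeated event does not say where a missing grade ranks.

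**Step 2. What would happen to an ungraded fatal TEAE?** It would be counted under "Treatment-Emergent Adverse Events leading to Death" but not in the Grade 4 or higher summary in the same list, although Protocol Table 7-1 defines Grade 5 as fatal. For a life-threatening event, the SAE definition in Protocol 7.1.2 requires that the subject was at risk of death when the event occurred. That is at least as strict as the potential threat to life in the Table 7-1 description of Grade 4.

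**Step 3. The plan's own precision figure.** SAP 1.4 gives a 95% CI half-width of at most 10% at n = 120 for an observed Grade ≥4 rate of 20% to 40%. Two formulas were used:

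- Wald: 1.96 × √(p(1 − p)/n).
- Clopper-Pearson: half of U − L, where L is the 0.025 quantile of Beta(x, n − x + 1) and U is the 0.975 quantile of Beta(x + 1, n − x).

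| Rate | x/120 | Wald half-width | Exact half-width |
|---|---|---|---|
| 20% | 24 | 7.2 points | 7.5 points |
| 30% | 36 | 8.2 points | 8.5 points |
| 40% | 48 | 8.8 points | 9.1 points |

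The stated figure reproduces, and this point does not dispute it.

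**Step 4. Size of the effect.** The endpoint counts subjects. An ungraded event changes it only if the subject has no other Grade ≥4 TEAE. Let k be the number of such subjects in an arm; the shift is k/n.

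- Planned Arms A and C: 1/120 = 0.83 points per subject.
- Arm B, about 26 subjects: 1/26 = 3.8 points per subject.

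For illustration, take a base rate near the 23/72 = 32% that Protocol 1.3 reports for Study 101-09. The values of k are assumptions; the documents give none.

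| n | k = 0 | k = 1 | k = 2 |
|---|---|---|---|
| 120 | 38/120 = 31.7% (23.5 to 40.8) | 39/120 = 32.5% (24.2 to 41.7) | 40/120 = 33.3% (25.0 to 42.5) |
| 26 | 8/26 = 30.8% (14.3 to 51.8) | 9/26 = 34.6% (17.2 to 55.7) | 10/26 = 38.5% (20.2 to 59.4) |

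Intervals are exact 95%. At n = 120, one subject moves the rate by about a tenth of the exact half-width (0.83 against 7.5 to 9.1 points).

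**The case against.** The strongest reply is that fatal and life-threatening events are the least likely to stay ungraded. The investigator is responsible for severity and for final confirmation of event information (Protocol 7.2). Table 7-1 supplies a grade where CTCAE has no criterion. Discrepancies are queried and forms confirmed before lock (Protocol 9.1.6). Hospital and autopsy records for such events can be requested (Protocol 7.3.1), and SAEs are reconciled with the safety database (SAP 7.1.4). This stands, and it is why the point is minor. It does not remove the gap: none of these steps is a rule for an event that is still ungraded at analysis.

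A second reply is that a separate category is transparent and neutral. Relationship has two values, so a worst-case default is simple. Severity has five, and an ungraded event with no other information could be any of them. This also stands for events about which nothing else is known, so a count that treats all of them as Grade ≥4 is only an upper bound. It does not cover events whose outcome or seriousness already gives the answer.

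Three stronger readings are tempting, and the documents do not support them:

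- A reader might infer that the sponsor accepts ungraded fatal events, because SAP 2.3 allows the final analysis once "outstanding data queries have been resolved or adjudicated as unresolvable". That is a general statement about data queries and says nothing about grades.
- A reader might call the death table and the Grade 4 or higher table contradictory. They would differ only if an ungraded fatal event occurred. The missing category and the death outputs would then make the gap visible and should prompt a query.
- A reader might want an ungraded laboratory event to take the programmed grade of the result nearest onset. That fits poorly with the maximum-intensity convention in Protocol 7.2.2 and the worst-grade convention in SAP 7.2.1. Protocol 7.1.3 also asks for the syndrome rather than the laboratory result where one applies, so matching events to values is not simple.

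**Conclusion.** The point holds as a minor gap. When triggered, the stated rule gives a Grade ≥4 count that disagrees with the protocol's own definitions of Grades 4 and 5, and the error can only run in the favourable direction. Its size is 0.83 points per affected subject at the planned 120 and 3.8 points at about 26. The study ended early (SAP 1) and the documents give no final arm sizes; if Arms A or C fell short of 120, the shift per subject there is larger than 0.83 points.

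The total effect cannot be computed, because neither document gives the number of ungraded events. It would be wrong to infer that known Grade 4 or 5 events have been dropped: nothing shows that any such event exists. There is no effect on type I error or power, since nothing is tested.

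**What to change.** Add to SAP 7.1.2, for the Grade ≥4 endpoint only:

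- An ungraded TEAE with a fatal outcome counts as Grade 5.
- An ungraded TEAE reported as an SAE under the life-threatening criterion counts as at least Grade 4.
- The number of subjects with TEAEs still ungraded after these rules is shown by arm, with a sensitivity count that treats those TEAEs as Grade ≥4, labelled as an upper bound.

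Tie the first rule to the outcome of the adverse event rather than to the list of all deaths, because Protocol 7.4.1 keeps unrelated deaths from progression out of SAE reporting.

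The cost is two or three sentences and a short derivation. A fatal outcome must already be available, since TEAEs leading to death are summarised. The case report form is not in the documents, so the sponsor should confirm that the life-threatening criterion is held as a separate field. The downside is that the Grade ≥4 rate may become slightly less favourable. If no grades are missing, nothing changes and the report can say so. SAP 1 already provides for documenting changes made after finalization in the clinical study report.
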